# **Summary of Amended Sections**

SAP Section(s)/ Purpose	Initial text from SAP version 2.0	Rationale / Updated text
Section 6.1.5 – Analysis Visit Windows / Assessment selection	No rules specified for the selection of assessments where multiple assessments may be eligible for tables except for Week 8 assessment.	Rules for selection of assessments used in Week 8 assessment of MAS remission provided in section 6.1.5, however no information provided for other safety and efficacy analysis and timepoint.  /  "In case there are two (or more) assessments from a subject within
		the visit window, the assessment with the date closest to the expected visit date will be used for the efficacy and safety analysis. In the event that two assessments are available and equidistant from the expected visit date, the result from earliest assessment will be used. If there are still two or more assessments recorded during the same day, the earliest measurement before the emapalumab infusion will be used (not applicable for the assessment of MAS remission at Week 8). If there is no treatment on the selected day, the earliest assessment of the selected day will be selected (not applicable for the
		assessment of MAS remission at Week 8). If there is no possibility to identify the earliest assessment, the assessment with the earliest sequence number will be used."

AD-ST-33.06 Effective date: 12-Nov-2020

[figure not shown]
Version 2.0 | Date 22-Jul-2021 | AD-PR-109.02 Effective date: 17-Aug-2020 Page 5 of 18

SAP Section(s)/ Purpose	Initial text from SAP version 2.0	Rationale / Updated text
Section 6.1.7 - Derived variables/ New Age group variable	No age group was defined in the SAP version 2.0.	Results will be posted and published in Eudra CT and predefined age group should be displayed as per template, therefore age group variable will be created and presented in the demographic table.  /  The new age group variable will be defined as follows  Age Group Definition  Newborns (0- 0 \leq (Date of 27 days) informed consent - Date of Birth) \leq 27  Infant and 28 \leq (Date of toddlers (28 informed consent - days - 23 Date of Birth) and months) age in years = 1  Children (2- 2 <= age in years = 1  Children (2- 12 <= age in years <= 11 years) 11  Adolescents 12 <= age in years <= 17 years)
		From 18-64 18<= age in years years <= 64
		From 65-84 65 <= age in years years <= 84
		Over 85 85 <= age in years years

[figure not shown]
Version 2.0 | Date 22-Jul-2021 | AD-PR-109.02 Effective date: 17-Aug-2020 Page 6 of 18

Section 6.1.7 - Derived variables/ IRR with missing start date	"If the onset time of the AE or the start time of the infusion is missing, then an AE with an onset date equal to an infusion date or infusion date + 1 will be considered for the assessment of IRRs."	Describe how completely missing AE start date will be imputed for an IRR assessment.  Corrected to "If the onset time of the AE or the start time of the infusion is missing, then an AE with an onset date equal to an infusion date or infusion date + 1 will be considered for the assessment of IRRs. If the onset date of the AE is completely missing, the AE will be considered as IRR (most conservative approach)."
Section 6.1.7 - Derived variables/ Infection definition	"Infection = any TEAEs part of the SOC 'infection and infestation'"	Infection definition updated to a broader search strategy for all potential infections with emapalumab use.  /  Updated to Infection = All AEs in the SOC "Infections and infestations" or in the HLGT "Microbiology and serology investigations".
Section 6.1.7 - Derived variables/ Selection of systemic glucocorticoid dose	"Select concomitant medications with ATC code H02B"	Selection should be applied on ATC code H02AB. The ATC level 4 H02AB correctly and specifically corresponds to GLUCOCORTICOIDS, whereas in the SAP version 2.0, selection by code H02B is an error, as this code does not include plain glucocorticoid products, but only combinations (CORTICOSTEROIDS FOR SYSTEMIC USE, COMBINATIONS).

[figure not shown]
 Version 2.0
 Date 22-Jul-2021
 AD-PR-109.02
 Effective date: 17-Aug-2020
 Page 7 of 18

		1
		Corrected to "Select medications with ATC Level 4 code H02AB"
Section 6.1.7 – Derived variables/ Steps to calculate the prednisone	"4) Select the weight in kg from the physical examination visit closest to the glucocorticoids administration date."	Further clarification on which assessment should be selected if observations are equidistant and prior to first treatment administration.
equivalent dose (mg/kg/day)		Under the Steps to calculate the prednisone equivalent dose (mg/kg/day), corrected to:
		"4) Select the weight in kg from the physical examination visit closest to the glucocorticoids administration date. If there are 2 such observations that are equidistant from the glucocorticoids administration date, the first observation will be selected. Prior to first treatment administration, the weight at screening will be selected."
Section 6.1.7 – Derived variables/ Steps to calculate the prednisone equivalent dose (mg/kg/day) and total daily doses	No specification of time frame for calculation of equivalent prednisone dose or total daily doses of anakinra, canakinumab, ciclosporin, etoposide, methotrexate, and tocilizumab.	To add detail on when equivalent daily dose of prednisone, and daily total doses of anakinra, canakinumab, ciclosporin, etoposide, methotrexate, and tocilizumab will be derived.
of anakinra, canakinumab, ciclosporin, etoposide, methotrexate, and tocilizumab		Specifications added: "Equivalent daily dose of prednisone, and daily total doses of anakinra, canakinumab, ciclosporin, etoposide, methotrexate, and tocilizumab will be derived from study day -180 until the end of the study."

[figure not shown]
 Version 2.0
 Date 22-Jul-2021
 AD-PR-109.02
 Effective date: 17-Aug-2020
 Page 8 of 18

Section 6.1.7 - "where the conversion factor is:  Derived 1 for prednisone	The use of dexamethasone was
variables/ Conversion factor for derivation of equivalent dose of prednisone  1.25 for methylprednisolone 1 for prednisolone"	not considered initially and should be added as administered to some patients.  /  Corrected to "where the conversion factor is:
	1 for prednisone
	1.25 for methylprednisolone
	1 for prednisolone 6 for dexamethasone"
Section 6.1.7 - Derived variables/ MAS remission  "The MAS remission evaluation is based on combination of assessments, including Investigator assessment and laboratory finding The latest date of assessments, within the view window of $\pm$ 3 days around the planned day the visit, will be used for the calculation of time to MAS remission."	To clarify assessment handling for the MAS remission. Currently in the SAP, it specifies "If one or more laboratory data are unavailable within the visit window" but no details on the visit windows.  /  Updated to: "The MAS remission evaluation is based on a combination of assessments, including Investigator assessment and laboratory findings, and will only be calculated if the Investigator assessment has been

[figure not shown]
 Version 2.0
 Date 22-Jul-2021
 AD-PR-109.02
 Effective date: 17-Aug-2020
 Page 9 of 18

	T	<del>-</del>
Section 6.1.7 – Derived variables/ Definition of Biologics	No specification of biologics concomitant used is specified in the SAP version 2.0.	Concomitant use of relevant biologics will be also summarized per section 9.6 however no specification was provided under section 6.1.7.  /  Specifications added: "Relevant concomitant biologics medications will be defined as medications from ATC 4 levels L04AB, L04AC."
Section 6.1.8 - Data Adjustments/Han dling/Convention s/ Handling partial or missing start/stop dates for equivalent daily dose of prednisone, and daily total doses of anakinra, canakinumab, ciclosporin, etoposide, methotrexate, and tocilizumab	No details regarding how to handle partial or missing start/stop dates for equivalent daily dose of prednisone, and daily total doses of anakinra, canakinumab, ciclosporin, etoposide, methotrexate, and tocilizumab	To add detail on how to handle partial or missing start/stop dates for equivalent daily dose of prednisone, and daily total doses of anakinra, canakinumab, ciclosporin, etoposide, methotrexate, and tocilizumab.  /  Imputation of partial/missing medication start or stop dates for equivalent daily dose of prednisone and daily total doses of anakinra, canakinumab, ciclosporin, etoposide, methotrexate, and tocilizumab: -Partial medication end date  • If only month and year are available, medication end date will be imputed to the last day of the corresponding month  • If only year is available, medication end date will be imputed to the 31st of December of the corresponding year -Partial medication start date  • If only month and year are available, medication start date  • If only month and year are available, medication start date

[figure not shown]
Version 2.0 | Date 22-Jul-2021 | AD-PR-109.02 Effective date: 17-Aug-2020 Page 10 of 18

date will be imputed to the
1st day of the
corresponding month
• If only year is available,
medication start date will
be imputed to the 1st of
January of the
corresponding year.
-Medication start and end dates are
both missing, then the record of the
medication will not be considered
(i.e. no derivation of equivalent
dose of prednisone or daily dose of
anakinra,).
-Medication end date is missing
(and medication start date not
missing)
• When medication end date
is missing and "Ongoing" is not ticked
If medication start
date < Study day -
180, then this
record will not be
considered (i.e. no
derivation of
equivalent dose of
prednisone or daily
dose of anakinra,
).
■ If Study day -180 ≤
medication start
date < Study day 0,
then medication
end date is set to
medication start
date.
• If medication start
$date \ge Study day 0,$
then medication
end date is set to
end of study date of

[figure not shown]
Version 2.0 | Date 22-Jul-2021 | AD-PR-109.02 Effective date: 17-Aug-2020 Page 11 of 18

		the corresponding patient.  • When "Ongoing" is ticked, then medication end date is set to end of study date of the corresponding patient unless medication start date > end of study date then set to medication start date of the corresponding patient.  -Medication start date is missing (and Medication end date is not missing)  • If medication end date < Study day -180, then this record will not be considered (i.e. no derivation of equivalent dose of prednisone or daily dose of anakinra,).  • If medication end date ≥ Study day -180, then the medication start date will be set to the medication end date.  Note: medication end date if available should have priority over
		the ongoing flag.
Section 6.1.8 - Data Adjustments/ Handling/ Conventions/ Handling < LLOQ, > ULOQ	No details regarding how the laboratory data below or above the limit of quantification will be handled.	Imputation rules to be applied to shift table when laboratory data below or above the limit of quantification. Laboratory listings will present data as collected.  / Imputation rules added: "Values
		below the lower limit of quantitation (i.e. < LLOQ) for individual values will be imputed to zeros when summarizing for

[figure not shown]
 Version 2.0
 Date 22-Jul-2021
 AD-PR-109.02
 Effective date: 17-Aug-2020
 Page 12 of 18

		descriptive statistics. Values above the upper limit of quantitation (i.e. > ULOQ) for individual values will be imputed to ULOQ values when summarizing for descriptive statistics."
Section 7.2 – Protocol Deviations / Correction	"Relevant protocol deviations categorized as major and minor will be tabulated in a summary table. Individual major and minor protocol deviations will be listed by patient."	Change in category terminology (applicable to the classification of deviations from a study conduct perspective) to align with references in regulations ICH E3 Q&A R1 and ICH GCP E6 R2.
		Corrected to: "Relevant protocol deviations categorized as important and non important will be tabulated in a summary table. Individual important and non important protocol deviations will be listed by patient."
Section 7.3 - Demographics and Other Baseline Characteristics /	"Summary statistics for age, sex, race, country of origin, height, weight, and body surface area (BSA) will be presented."	Pre-defined age group, as defined per Eudra CT publishing template, was added (see Section 6.1.7) and will be summarized in the demographic table.
New Age group variable		Updated to: "Summary statistics for age (as continuous and categorical variables), sex, race, country of origin, height, weight, and body surface area (BSA) will be presented."
Section 9.1.2 – Deaths and Serious Adverse Events/	"Serious adverse events will be tabulated by:"	Corrected to:  "Serious TEAEs will be tabulated by:"
Correction		
Section 6.1.8 – Data	Section 6.1.8 states "Adverse events will be coded using the latest version of the Medical Dictionary	Correction of the MedDRA version.

[figure not shown]
Version 2.0 | Date 22-Jul-2021 | AD-PR-109.02 Effective date: 17-Aug-2020 Page 13 of 18

Adjustments/ Handling/ Conventions and Section 9.1 – Adverse Events / Correction	for Regulatory Activities (MedDRA)."  Section 9.1 states "All AEs, TEAEs, and SAEs will be coded using the latest version of MedDRA."	Corrected to:  Section 6.1.8: "Adverse events will be coded using Medical Dictionary for Regulatory Activities (MedDRA) version 23.0."  Section 9.1: "All AEs, TEAEs, and SAEs will be coded using MedDRA version 23.0."
Section 9.3 – Vital signs/ Temperature presented per route	No details regarding how the temperature will be presented.	As temperature could be measured at different location, summary statistics and change from baseline should consider the location/route.  /  Sentence added: "Highest daily body temperature will be presented by route; shift tables will display baseline and post-baseline body temperatures from the same route."
Sections 9.6 – Concomitant Medication / Remove of Concomitant Medications Administered for the Treatment of sJIA analysis	"Concomitant Medications Administered for the Treatment of sJIA will be also summarized and presented separately."	A number of medications can be administered to treat both sJIA and MAS. The investigators may record either sJIA or MAS (or both) as indication for their use. A summary table presenting only medications administered to treat sJIA may provide partial and potentially misleading information. All concomitant medications with their reported indications will be presented in listings. It was decided that the following sentence will be removed:  "Concomitant medication administered for the treatment of sJIA will be also summarized and presented separately."

[figure not shown]
Version 2.0 | Date 22-Jul-2021 | AD-PR-109.02 Effective date: 17-Aug-2020 Page 14 of 18

[figure not shown]
Section 9.6 – Concomitant Medication/ WHO-DD version correction	"Medications will be coded using anatomical therapeutic chemical (ATC) classification level 2 (World Health Organization Drug Dictionary [WHO-DD] Version 2019)."	Correction of the WHO-DD version  / Corrected to:  "Medications will be coded using anatomical therapeutic chemical (ATC) classification level 2 (World Health Organization Drug Dictionary [WHO-DD] Version March 2020)."
Section 12.1 – Patient profile report/ Removal of DOB	"Header: subject identification number, sex, study site, date of birth, age at screening."	As described for Section 15.2, Date of birth (DOB) is protected information under the GDPR, therefore the DOB was removed from the patient profile.  /  Corrected to: "Header: subject identification number, sex, study site, age at screening (years)."
Section 14.1, Table 5 – Safety Data/ Remove of Concomitant Medications Administered for the Treatment of sJIA table	Concomitant Medications Administered for the Treatment of sJIA by ATC Level 2 and Preferred Term	As detailed for Section 9.6, the table on Concomitant Medications Administered for the Treatment of sJIA by ATC Level 2 and Preferred Term will be removed.  / Remove Table 14.3.6.2.2 from the list of Tables.
Section 14.1, Table 5 – Safety Data/ Update Concomitant use of Biologics	"Concomitant use of Biologics by ATC Level 2 and Preferred Term"	Display by ATC level 4 instead on ATC level 2 as selection of medications are based on ATC Level 4.  /  Corrected to: "Concomitant use of Biologics by ATC Level 4 and Preferred Term"
Section 14.3 –	Figures 14.2.6, 14.2.7, 14.2.8, described as	Per section 8.1, "The efficacy

 Version 2.0
 Date 22-Jul-2021
 AD-PR-109.02
 Effective date: 17-Aug-2020
 Page 15 of 18

Planned Figure Descriptions/ Update populations	Kaplan Meier curves, will be produced on the All Treated Population per the Population column.	analysis will be based on the All Treated Population. Efficacy analyses will be repeated for the EVAL Population."; figures should also be produced on the Evaluable Population  / Corrected to: "All Treated Population, All Evaluable Population"
Section 15.2 – Figure 1: Patient Profile Shells/ Remove DOB from the Patient Profile		Date of birth (DOB) is protected information under the GDPR. The age in years is sufficient and there is no need to present the DOB.  Removal of Date of Birth in the header of Patient Profile as age in years is sufficient.

[figure not shown]

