### 6.1.7. Derived Variables

- Change from baseline = value at current time point value at baseline.
- Conversion factors: The following conversion factors will be used to convert days into months or years:
  - $\circ$  1 month = 30.4375 days
  - $\circ$  1 year = 365.25 days

AD-ST-33.04 Effective date: 30-Jun-2017

Version 2.0 | Date 29-Oct-2020 | AD-PR-109.01 Effective date: 26-Jun-2017

- Treatment-emergent AE (TEAE) = any adverse event with an onset date/time after the start of the first emapalumab administration.
- Infusion-related reactions (IRRs) = any TEAE that is reported to have occurred within 24 hours after start of infusion and assessed as related to study treatment by the Investigator, excluding the following system organ classes (SOCs): "Infections and infestations," "Congenital familial and genetic disorders," "Neoplasms benign, malignant and unspecified (incl. cysts and polyps)," "Product issues," "Social circumstances," and "Surgical and medical procedures."

If the onset time of the AE or the start time of the infusion is missing, then an AE with an onset date equal to an infusion date or infusion date + 1 will be considered for the assessment of IRRs.

- Infection: any TEAEs part of the SOC 'infection and infestation'.
- Duration of exposure (days) = date last study drug intake date first study drug intake + 1
- Study Day = date of interest date of first emapalumab infusion.

This SAP follows the protocol assumption that the day of the first infusion is SD0. Starting with 0, rather than with 1, can cause trouble for SDTM programming since it is not compliant with the SDTM Implementation Guide. SDTM data set will include two ways in counting the study day: starting with zero as in the protocol and starting with 1 as reccommended by the SDTM Inplementation Guide.

- Cumulative administered dose of emapalumab (mg/kg) = sum of administered emapalumab doses (mg/kg)
- Average administered dose of emapalumab (mg/kg) = (cumulative dose of emapalumab)/(number of doses)
- Equivalent dose of prednisone

The Systemic Glucocorticoids data are collected into two modules of the paper CRF:

- the 'Systemic Glucocorticoids from SD-3 until SD15" log
- the 'Concomitant Medication' log

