#### 6.1.8. Data Adjustments/Handling/Conventions

All collected data will be presented in listings. Data not subject to analysis according to this plan will not appear in any tables or graphs but rather in the data listings only.

Adverse events will be coded using the latest version of the Medical Dictionary for Regulatory Activities (MedDRA).

For TEAEs:

AD-ST-33.04 Effective date: 30-Jun-2017

Version 2.0 | Date 29-Oct-2020 | AD-PR-109.01 Effective date: 26-Jun-2017

Page 25 of 51

- If an AE with partial time occurs on the same day of the first infusion then the AE will be considered a TEAE.
- If an AE has missing date then the AE will be considered a TEAE.
- If partial dates of AE occur, the convention for replacing missing dates for the purpose of discriminate TEAE is as follows:
  - If just day is missing then the AE will be considered a TEAE when the mm/year of AE is the same of after the mm/year of the first infusion;
  - If just month is missing then the AE will be considered a TEAE when the year of AE is the same or after the year of the first infusion.

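### As worded, the errata makes an AE with no onset date an infusion-related reaction outright, bypassing the relatedness and organ-class conditions

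*SAP*

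**What the plan says.** SAP 6.1.7 (Derived Variables) defines an IRR as "any TEAE that is reported to have occurred within 24 hours after start of infusion and assessed as related to study treatment by the Investigator," and then removes six MedDRA system organ classes, infections among them. So there are three requirements beyond treatment-emergence: timing, relatedness and organ class.

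Where only a clock time is missing, the SAP uses dates instead, and the errata keeps this rule: "then an AE with an onset date equal to an infusion date or infusion date + 1 will be considered for the assessment of IRRs". That makes the event a candidate, and relatedness and organ class still decide.

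SAP Errata v2.0 (Summary of Amended Sections, row on IRRs with a missing start date) then adds a sentence for the case of no date at all: "If the onset date of the AE is completely missing, the AE will be considered as IRR (most conservative approach". The row gives its purpose as: "Describe how completely missing AE start date will be imputed for an IRR assessment".

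Separately, SAP 6.1.8 says: "If an AE has missing date then the AE will be considered a TEAE". No stop-date check accompanies that rule.

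**The concern.** Two adjacent sentences use different language for two degrees of the same problem. A missing time means the event "will be considered for the assessment of IRRs". A missing date means that it is classified as an IRR. A programmer following the second sentence would flag every undated AE, whatever the Investigator recorded about causality and whatever its organ class.

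Relatedness and organ class do not depend on the date. Relatedness is recorded by the Investigator and organ class comes from coding, so neither needs imputing when the onset date is absent.

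Protocol 10.2 gives IRRs special attention, SAP section 11 reports them as an addition to the safety endpoints, and SAP 9.1.3 tabulates them by preferred term and maximum severity. The background experience in Protocol 10.5.2.2 is no serious or severe infusion reaction, and mild or moderate rashes in under 2% of infusions. Against that background, one wrongly classified event could change how a small IRR table reads. An undated infection would appear in both the infection table and the IRR table, although the IRR definition excludes that organ class.

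**Working it through.** The plan gives no figure to reproduce. The check is on a classification rule, followed by the scale of its effect.

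**Step 1. Classify every type of undated AE.** The inputs are the IRR definition (SAP 6.1.7), the errata sentence and the missing-date rule (SAP 6.1.8). Under 6.1.8 every undated AE is treatment-emergent, so that condition screens nothing out. Three facts about the event remain: related or not, excluded organ class or not, and truly pre-treatment or not. That gives 2 × 2 × 2 = 8 combinations. The last column treats the missing date as meeting the 24-hour condition only.

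| Related | Excluded class | Truly pre-treatment | Errata, literal | Timing only |
|---|---|---|---|---|
| yes | no | no | IRR | IRR |
| yes | no | yes | IRR | IRR |
| yes | yes | no | IRR | no |
| yes | yes | yes | IRR | no |
| no | no | no | IRR | no |
| no | no | yes | IRR | no |
| no | yes | no | IRR | no |
| no | yes | yes | IRR | no |

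The literal rule makes 8 of 8 an IRR. The timing-only rule makes 2 of 8 an IRR. The other 6 fail the SAP's own definition on relatedness, organ class or both.

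The second row shows a separate point. A related pre-treatment event still gets in under timing-only imputation, because 6.1.8 has already made it treatment-emergent. Only a stop-date check can remove it, and only when a stop date was recorded.

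**Step 2. Scale.** SAP 3.2 plans about 12 patients. SAP 9.1.3 asks only for counts and percentages of IRRs, so the exact (Clopper-Pearson) intervals here are added to show scale. For x patients out of n, the lower limit is the 2.5% quantile of Beta(x, n − x + 1) and the upper limit is the 97.5% quantile of Beta(x + 1, n − x).

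- x = 0, n = 12: 0%, upper limit 1 − 0.025^(1/12) = 26.5%.
- x = 1, n = 12: 1/12 = 8.3%, lower limit 1 − 0.975^(1/12) = 0.2%, upper limit 38.5%.
- x = 2, n = 12: 2/12 = 16.7%, interval 2.1 to 48.4%.

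SAP 6.1.4 replaces some withdrawn patients, so the All Treated denominator could exceed 12. With 14 patients, an assumed figure, one patient gives 1/14 = 7.1% (0.2 to 33.9%), against 0/14 (0 to 23.2%).

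The values of x are illustrations. The documents give no count of undated AEs.

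**The case against.** **Intent.** The row says that it is imputing a start date for an assessment, and it amends only the missing-time paragraph. The base definition is not deleted, so the authors may well have meant timing only. This stands as a reading of intent. It does not rescue the wording, which states a classification and is labelled the most conservative choice. If timing only was meant, the sentence should say so.

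**The protocol is broader.** Protocol 10.2 describes IRRs by timing alone, with no relatedness or organ-class condition, and SAP 9.1 assumes the worst case for missing severity or relationship. Both are true. But the SAP chose a narrower definition for its table, and the 9.1 rule fills values that are missing. The errata sentence, read literally, sets aside values that were recorded.

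**It should seldom apply.** Patients stay in hospital until at least SD15 (Protocol 3.1), blank CRF fields are not allowed (15.1), monitoring is at least every 14 days while patients are enrolled (13.2), and onset date is part of the minimum initial SAE report (10.3.2). IRRs are listed by patient, the analysis is descriptive, and no test or stopping rule uses IRR incidence. All of this stands and limits the expected impact.

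**Stronger readings.** A reader might infer that the errata sentence by itself lets pre-treatment events into the IRR table. It does so only jointly with SAP 6.1.8. A reader might also infer that misclassified events would rival the genuine IRRs in number. That would need a total AE count and a missing-date rate, and neither is in the documents. The under-2% figure is a rash rate per infusion in HLH patients, not a forecast under this IRR definition.

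**Conclusion.** The point holds as a correction to a stated rule, and it is minor. Taken literally, the errata sentence puts undated AEs judged unrelated, and undated AEs in excluded organ classes, into the IRR table, against the definition that it is meant to serve. The conservative label does not justify discarding recorded relatedness and organ class.

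Each affected patient adds 8.3 percentage points at n = 12, if that patient has no other IRR. The realised effect depends on how many AEs have no onset date at all, which may be zero.

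**What to change.** Replace the errata sentence with: *If the onset date is completely missing, the 24-hour timing condition is taken as met, unless a recorded stop date is before the first infusion; the relatedness and SOC conditions still apply.*

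Add the same stop-date check to the missing-date rule for TEAEs in SAP 6.1.8, so that the two derivations agree. The errata already uses an end-date check of this kind for medications with a missing start date. Flag undated events in Listing 16.2.9.15 so that a reader can see which IRRs rest on imputed timing.

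The cost is one sentence in the errata, one clause in 6.1.8 and a small programming change. The downside is a slightly less conservative rule for undated AEs. A related pre-treatment event with no recorded stop date would still be counted.

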## 10.3 RECORDING AND REPORTING SAFETY PARAMETERS

### 10.3.1 Adverse events

Adverse events (AEs) are defined as any undesirable experience occurring to a subject during the study, whether or not considered related to the IMP. All AEs reported by the patients or his/her relatives or observed by the Investigator or his staff during the clinical study from the signature of the ICF up to and including the EoS visit will be reported on the AE data collection form.

Medical conditions present at screening (before ICF signature) should be recorded in the medical history section of the CRF.

All AEs will be reported in the appropriate section of the CRF.

An AE which occurs between start of screening visit (after ICF signature) and start of first IMP administration will be considered as a pre-treatment AE.

Any AE that occurs after the start of the first IMP administration will be considered in the study as Treatment Emergent Adverse Event (TEAE).

However, if a pre-existing medical condition recorded in the medical history worsens (clinically significant change in intensity or frequency), it must be recorded as an AE in the CRF and, depending on the time of its occurrence, will be considered as a pre-treatment AE or a TEAE. If a medical condition, recorded as a pre-treatment AE, worsens it will be recorded in the CRF as a separate TEAE.

For each AE, the following will be assessed and recorded: intensity, relationship to the IMP, action taken regarding the IMP, any treatment received for the event and outcome of AE to date.

Intensity of AEs will be graded on a three-points scale (mild, moderate, severe) using the modified WHO (World Health Organization) toxicity scale (Grade 3 and 4 are considered to be the severe grade). If AE severity cannot be assessed by this scale, assessment by the Investigator should be made using the following definitions:

- Mild: discomfort noticed but no disruption of normal activity,
- Moderate: discomfort sufficient to reduce or affect normal daily activity,
- Severe: inability to work or perform normal daily activity.

For a given AE, the assessment of its intensity should reflect the highest grade (on the 3 points scale mentioned above) reported during its course (except when the intensity of a pre-treatment AE increases after treatment initiation, as indicated above).

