#### 9.1.4. Infections

The number and percentages of patients reporting infections and number of events, displayed by MedDRA PT, and will be tabulated in total and by maximum severity.

A by-patient listing of all infections will be displayed with date of sampling, pathogen, source, type of investigation, result (positive, negative, numerical value and units), and the AE it was linked to.

AD-ST-33.04 Effective date: 30-Jun-2017

Version 2.0 | Date 29-Oct-2020 | AD-PR-109.01 Effective date: 26-Jun-2017

Page 30 of 51

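### The errata drops the treatment-emergent condition from the infection definition, so infections arising between consent and the first dose enter the dedicated infection table

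*SAP*

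**What the plan says.** SAP v2.0, Section 6.1.7, defines the class as "Infection: any TEAEs part of the SOC 'infection and infestation", and a TEAE as "any adverse event with an onset date/time after the start of the first emapalumab administration".

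The Summary of Amended Sections in SAP Errata v2.0 replaces the infection definition: "Infection = All AEs in the SOC" Infections and infestations or in the HLGT Microbiology and serology investigations. The rationale reads "Infection definition updated to a broader search strategy for all potential infections with emapalumab use". It does not mention the time window.

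Protocol Section 10.3.1 collects adverse events from signature of the consent form to the end-of-study visit. An event arising between screening and the "start of first IMP administration will be considered as a pre-treatment AE". Conditions already present before consent belong in medical history, unless they worsen.

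SAP Section 9.1.4 then tabulates "The number and percentages of patients reporting infections and number of events" by preferred term and maximum severity. The planned output is Table 14.3.2.4, on the All Treated Population, and its title carries no treatment-emergent restriction.

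**The concern.** In SAP v2.0 the treatment-emergent condition for infections sat only in the definition. The errata made two changes at once: it widened the set of coded terms, and it removed the time condition. Only the first is explained. With the condition gone, nothing in 9.1.4 or in the title of Table 14.3.2.4 keeps a pre-dose infection out of a table that will be read as describing infections on emapalumab.

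This also makes infection the exception in the plan. The AE incidence tables by SOC and PT use TEAEs, infusion-related reactions are defined from TEAEs, and the same errata corrects the SAE tabulation to serious TEAEs. Yet infection is the AE class that the safety endpoint in both documents singles out for particular attention. What is at stake is the meaning of the percentages, event counts and maximum severities in that one table and its listing.

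**Working it through.** The documents state no figure on this point, so there is none to reproduce. The check follows one event through the definitions.

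**Step 1. Which events change status?** Take an infection AE by time of onset.

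| Onset | Recorded as | Counted under SAP v2.0 | Counted under Errata v2.0 |
|---|---|---|---|
| Before consent, no worsening | Medical history | No | No |
| New or worsening after consent, before first dose | Pre-treatment AE | No | **Yes** |
| After start of first dose | TEAE | Yes | Yes |

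Only the middle row changes. Protocol Section 3.2 puts screening within one week before the first infusion, so that is the length of the window.

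**Step 2. Does another filter catch it?** SAP 9.1.4 has none, and neither does the title of Table 14.3.2.4. The contents that 9.1.4 specifies for the infection listing (sampling date, pathogen, source, test, result, linked AE) include no treatment-emergence flag. The flag for non-TEAEs in SAP 9.1 belongs to the AE listing.

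**Step 3. Would restoring the condition lose on-drug infections?** No. SAP 6.1.8 treats an AE with a missing date as a TEAE. Protocol 10.3.1 records a pre-treatment AE that later worsens on treatment as a separate TEAE.

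**Step 4. Size per patient.** If k patients have infection AEs only before the first dose, the infection percentage rises by 100 × k/N points. For k = 1:

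- N = 12 (planned, approximately): 1/12 = 8.3 points
- N = 10: 1/10 = 10.0 points
- N = 14: 1/14 = 7.1 points

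A patient who also has an on-treatment infection adds nothing to the patient percentage. The event count still rises, and a more severe pre-dose episode of the same preferred term could set the maximum severity shown.

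**Step 5. How likely is at least one such event?** The documents give no rate. Let p be an assumed probability that a patient has a pre-dose infection AE, with patients independent. The chance of at least one in 12 is 1 − (1 − p)^12:

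- p = 0.05: 1 − 0.95^12 = 46%
- p = 0.10: 1 − 0.90^12 = 72%
- p = 0.20: 1 − 0.80^12 = 93%

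These values show sensitivity to p only. They do not estimate what happened in the trial.

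**The case against.** The best defence is that the change is deliberate and cautious. The rationale speaks of all potential infections, and the neighbouring errata row on infusion-related reactions takes an explicitly conservative line. The safety endpoint refers to AEs, not TEAEs. A pre-dose event can only raise the apparent infection percentage, so it cannot hide a signal. Everything is descriptive, and no decision rule uses this figure. The table shells are in a separate document, so a label or split by treatment emergence may exist there.

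Much of this stands as a limit on importance. It does not explain why events before any exposure should count as infections with emapalumab use. If capturing them was intended, a separate row would do it without mixing the two periods.

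Three stronger readings are tempting, and the documents do not support them:

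- *The table mixes MAS triggers with on-drug infections.* A trigger precedes MAS, which must be active at eligibility. An infection present before consent goes to medical history unless it worsens. An abnormal screening laboratory result becomes an AE only if it needs specific treatment or leads to a new diagnosis (Protocol 10.3.1).
- *About a third of patients could be affected.* The one-third figure in Protocol 1.2.1 is the share with an infectious trigger in a retrospective survey. It is not a rate of new infection AEs between consent and dosing.
- *The infection table cannot be reconciled with the TEAE tables.* TEAEs are tabulated by SOC and PT (Table 14.3.1.2.2) and by maximum severity (14.3.1.3), non-TEAEs have Table 14.3.1.6, and the AE listing flags events that are not treatment-emergent. With about 12 patients, a reader can separate the periods.

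**Conclusion.** The point holds as a defect in the current definition. Followed literally, Errata v2.0 counts infection AEs arising or worsening between consent and first dose in the dedicated infection outputs, and its stated rationale does not support that. Each patient whose only infection AE is pre-dose adds 8.3 points at N = 12; the number of such patients is unknown and may be zero. The conclusion assumes that the separate shells and programs apply the errata wording as written. The effect is limited to SAP 9.1.4, Table 14.3.2.4 and the infection listing. It is worth correcting because those outputs report the class of event under closest watch, but it leaves the general TEAE analysis intact.

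**What to change.** Define infection as any TEAE in the SOC Infections and infestations or the HLGT Microbiology and serology investigations. Show pre-treatment infections in a separate row of Table 14.3.2.4, or add a treatment-emergence flag to the infection listing (16.2.9.14). If counting pre-dose events was intended, say so in the errata and split the table by period. The cost is a wording change in the errata, one program filter, and a row or flag. The wider term search is kept and no on-drug infection is lost.
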